7.8 Unscheduled Visits

Aside from scheduled visits, participants may require an unscheduled visit either by telephone or in person at the clinical study site. All assessments will be performed according to Table 1: Schedule of Assessments . This visit will include, at a minimum:

- Assessment of AEs
- Complaints/device deficiencies since last visit
- Pump and CGM data review by clinician

Additional assessments, including review of BG/ketone meter data, may be warranted at the discretion of the investigator.

Unscheduled visits should be documented when there is meaningful contact with the subject, such as when updating device settings, subject retraining, or any in-person contact. Basic or minor contacts to discuss subject visit scheduling, device questions, subject reminders, requests for or providing additional supplies, or follow up activities related to another scheduled visit should not be documented as an Unscheduled Visit.

Instructions will be given to participants on how to contact clinical study staff 24 hours per day to report any study related problems. Participants will be encouraged to call the clinical study site at any time with any concerns.

7.9 Early Withdrawal

Any participant may withdraw from the study at any time for any reason. Upon withdrawal, assessments will be performed following Table 1: Schedule of Assessments and Table 2: Patient Reported Outcomes (Questionnaires). The investigator may also terminate a participant's participation in the study if it is in the best interest of the participant or if the Sponsor or local regulatory agency terminates the study.

The Early Withdrawal visit will include:

- A1C (central laboratory)
- Review of concomitant medications
- Weight
- Vital signs
- Assessment of AEs
- Insulin delivery metrics (e.g., TDI, average basal and bolus insulin dose, and time on device) (Control group only)
- Completion of questionnaires (Table 2: Patient Reported Outcomes (Questionnaires))
- Return BG meter, Ketone meter, and study CGM, if unused
- Return Omnipod 5 System (Intervention group only)
- Stop CGM data collection
- Data Portal discontinuation (Intervention group only)
- Complaints/device deficiencies such as occlusion alarms and system hazard alarms since last visit
- BG/ketone meter data review by clinician
- Pump and CGM data review by clinician

The reason for withdrawal will be recorded, and their participation in the study will end.

In the event of a participant's death during the study, the participant's participation will be considered terminated, and the date of death will be used as the date of study exit.

7.10 Lost to Follow-up

Every effort will be made to contact a participant in the event of a missed scheduled visit. A participant will be considered lost to follow-up if they are inaccessible by two or more

different methods of contact and fail to show up for two scheduled visits. The site will document each attempt made to contact the participant and specify the reason for early withdrawal as lost to follow-up.

8 SPONSOR REPRESENTATIVES

One or more representatives of the Sponsor may be present at the clinical study site during study visits under supervision of study site personnel.

9 SAFETY

9.1 Types of Known Risks and Benefits

There are known risks and benefits. Most of the risks are not unique to the study and are typical for patients using insulin pumps, CGM, and BG meters. For the Control group, the applicable Instructions for use (IFU) should be referenced for any additional potential risks.

The known risks are as follows:

- Hypoglycemia and/or hyperglycemia as a result of change in diet, activity, diabetes management or insulin regimen during the study.
- Hypoglycemia and/or hyperglycemia as a result of over or under delivery of insulin due to a device defect, failure or malfunction of any of the system components.
- Hypoglycemia, hyperglycemia, diabetic ketoacidosis, seizure, coma or death related to insulin administration, pump use or misuse, or Omnipod 5 System use or misuse.
- Use of the Pod – because the Pod uses only rapid-acting insulin, users are at increased risk for developing hyperglycemia if insulin delivery is interrupted. If it is untreated, prolonged hyperglycemia can lead to diabetic ketoacidosis (DKA). DKA can cause symptoms such as breathing difficulties, shock, coma, or death. Further, occlusions can interrupt insulin delivery and lead to hyperglycemia or DKA. Other potential risks associated with using the Pod are:
 - Anaphylaxis (allergic shock)
 - Bruising at the Pod site
 - Bleeding at the Pod site
 - Erythema (redness at the Pod site)
 - Excoriation (raw skin at Pod site)
 - Pruritus (itching)
 - Induration (hardening of the skin at the Pod site)
 - Infection (can include heat, redness, swelling, pain, and drainage)
 - Inflammation (redness, swelling)
 - Skin reaction to adhesive at the Pod site
 - Papule (small, solid raised area on the skin similar to a pimple)
 - Pain or discomfort
 - Ulceration (skin sores)
 - Vesicles (blisters)
- Use of the CGM – risk of bruising, infection, pain and/or bleeding at the site of insertion, and skin site reaction to adhesive

- Use of the Controller – risk of overheating of the Omnipod 5 Controller charging port and cable, including the cable melting, deforming, or discoloring. The excess heat may cause minor burns if those areas of the controller are touched or could lead to fire.
- On rare occasions, the CGM sensor may break and leave a small portion of the sensor under the skin that may cause redness, swelling, or pain at the insertion site, and may require surgical removal.
- Blood sampling with fingerstick – minor discomfort and risk of infection at site of fingerstick

There may be no direct benefits to participating in this study however knowledge will be gained that may benefit others. In addition, participants may experience improvements in glycemic control.

9.2 Hypoglycemia/Hyperglycemia

Participants will be asked to treat per their usual routine if they suspect either hypoglycemia or hyperglycemia, either by confirmation of hypoglycemia with a fingerstick BG, symptoms, or perceived risk.

Participants will be encouraged to manage their hyperglycemia per their usual routine. This includes checking for ketones and administering a correction bolus if needed.

In the event of unexplained hyperglycemia, where the CGM is $>300\text{mg/dL}$ for 1 hour or $>250\text{ mg/dL}$ for 2 hours, blood glucose (measured with BG meter) and ketones should be checked. If BG is $\geq 300\text{ mg/dL}$ and ketones are $>1.0\text{ mmol/L}$, an occlusion or dislodged cannula should be suspected. The Pod or infusion set should be removed, and the participant will be instructed to replace the Pod or infusion set at a different location on the body. Participants should contact the clinical site for further instructions to determine whether an additional injection of insulin is required. This prolonged hyperglycemic event, defined as meter BG $\geq 300\text{ mg/dL}$ and ketones $>1.0\text{ mmol/L}$, will be recorded as an adverse event.

9.3 Adverse Events

Adverse Event (AE): is defined as any untoward medical occurrence, unintended disease or injury, or any untoward clinical signs (including an abnormal laboratory finding) in participants, users or other persons, whether or not related to the investigational medical device.

NOTE 1: This includes events related to the investigational medical device or the comparator.²²

NOTE 2: This definition includes events related to the procedures involved (any procedure in the clinical investigation plan).²²

Serious Adverse Event (SAE): Any untoward medical occurrence that:

- Led to death
- Led to serious deterioration in the health of the participant, that either resulted in:

- a life-threatening illness or injury, or
 - a permanent impairment of a body structure or a body function, or
 - hospitalization, or prolonged existing hospitalization, or
 - medical or surgical intervention to prevent life-threatening illness or injury or permanent impairment to a body structure or a body function.
- Led to fetal distress, fetal death, or a congenital abnormality or birth defect.

NOTE: Planned hospitalization for a pre-existing condition, or a procedure required by the clinical investigational plan, without serious deterioration in health, is not considered a serious adverse event.²²

Unanticipated Serious Adverse Device Effect (USADE): Any serious adverse effect on health or safety or any life-threatening problem or death caused by, or associated with, a device, if that effect, problem, or death was not previously identified in nature, severity, or degree of incidence in the investigational plan or application (including a supplementary plan or application), or any other unanticipated serious problem associated with a device that relates to the rights, safety, or welfare of participants.²²

Adverse Device Effect (ADE): An adverse device effect (ADE) is an adverse event related to the use of an investigational medical device.²²

NOTE 1: This definition includes any adverse event resulting from insufficient or inadequate instructions for use, deployment, implantation, installation, or operation, or any malfunction of the investigational medical device.²²

NOTE 2: This definition includes any event resulting from user error or from intentional misuse of the investigational medical device.²²

An event that occurs solely due to participant (i.e., user) error in which the device functions properly generally will not be considered an ADE unless it is determined that the instructions on the screen of the device or user manual (or similar training materials) may have contributed to the event (note: the event may still meet criteria for reporting as an adverse event).

Serious Adverse Device Effect (SADE): A serious adverse device effect is defined as an adverse device effect that has resulted in any of the consequences characteristic of a serious adverse event.²²

Anticipated Serious Adverse Device Effect (ASADE): anticipated serious adverse device effect (ASADE) is an effect which by its nature, incidence, severity or outcome has been identified in the risk assessment.

Device Deficiency (DD): A device deficiency is defined as a device related complaint or malfunction or any inadequacy of a device with respect to its identity, quality, durability, reliability, safety or performance and includes misuse or use errors and inadequate labeling. A device deficiency is something that happens to a device or is related to device performance, whereas an adverse event happens to a participant. A device deficiency may occur independently from an AE, or along with an AE. An AE may occur without a device deficiency or there may be an AE related to a device deficiency.

For any event where there is suspicion that the Omnipod 5 study device is involved, the Sponsor will request that the investigator return the device component for evaluation.

All device deficiencies will be reported to the Sponsor within 3 business days of knowledge of the deficiency and documented on an appropriate eCRF. Once entered, notifications will be sent automatically to Sponsor. Alternate reporting methods will be provided to site for notifying Sponsor if database entry is inaccessible. All device components associated with a reported device deficiency (Controller, Pod, and CGM) should be retained at the clinical site and returned to the Sponsor or CGM manufacturer for investigation and analysis.

9.4 Reportable Adverse Events

Adverse events will be assessed on an ongoing basis throughout the study. Adverse event reporting will begin at the start time of the standard therapy (i.e., insertion of the CGM sensor) and continue until the participant's participation has ended. All adverse events must be followed until resolution, or until the AE has stabilized, or until the study has been completed.

Pre-existing medical conditions or symptoms observed prior to the start time of the standard therapy phase will not be recorded as an AE and should be collected in the participant's medical history. In the event there is a change (i.e., worsening) in the pre-existing medical condition or symptoms after enrollment meeting the criteria of a reportable adverse event, then an AE must be reported.

For this protocol, a reportable adverse event includes any untoward medical occurrence that meets one of the following criteria:

1. An SAE
2. An ADE unless excluded from reporting in Hypoglycemic Events and Hyperglycemic/Ketotic Events sections below
3. An AE not related to a study device issue which leads to temporary or permanent discontinuation of the study devices or the participant's own insulin pump, or creates a clinically significant impact on a participant's glucose control
4. An AE that affects the participant's ability to complete any study procedures
5. An AE for which a visit is made to a hospital emergency department
6. Hypoglycemic Events as defined below
7. Hyperglycemia/Ketotic Events as defined

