9.7 Relationship of Adverse Event to Devices or Study Procedures

The investigator will be responsible for deciding on the causal relationship of the AE. Specifically, the investigator will report whether the AE was related to study procedures and/or related to the devices (participant's own insulin pump, study CGM and Omnipod 5).

To ensure consistency of adverse event causality assessments, investigators should apply the following general guidelines when determining whether an adverse event is related.

The causal relationship to the study procedures and the devices for each adverse event will be rated as follows:

- Unrelated: The event is not related to the procedures or the investigational device.
- Possibly Related: The temporal sequence is such that the relationship is not unlikely or there is no contradicting evidence that can reasonably explain the participant's condition. There is a possibility of any relation between the event and the procedures or the devices.
- Related: The temporal sequence is relevant, or the event abates upon completion of the procedure/ use of devices, or the event cannot be reasonably explained by the participant's condition or comorbidities. The event is related or most likely associated with the procedures or the devices.

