6.5 ANALYSIS OF ADVERSE EVENTS

Safety summaries and analyses will be based on all participants that are randomized into the study (i.e., modified Intention to Treat analysis set). All adverse events reported over the course of the study will be summarized and tabulated by study phase (standard therapy vs. randomized period), event category, seriousness, severity, and relationship to the study procedures and the investigational device. Except where indicated, a participant reporting the same adverse event more than once will be counted once when calculating the number and percentage of participants with that particular event.

Adverse events leading to death or to discontinuation from the study will be listed separately. A listing of all adverse events will be provided. Adverse events for participants excluded from mITT analysis set will be listed separately.

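### Protocol 9.4 makes any adverse device effect of the investigational device reportable, but a non-serious event related to the participant's own pump only if it meets one of criteria 3 to 7, so descriptive counts of minor device-related events are not comparable between arms

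*Protocol*

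**What the plan says.** Protocol 9.4 limits adverse event reporting to seven criteria. Criterion 2 is "An ADE unless excluded from reporting in Hypoglycemic Events and Hyperglycemic/Ketotic Events sections below". It carries no test of seriousness or consequence beyond the glycemic exclusions. Protocol 9.3 defines the term: "An adverse device effect (ADE) is an adverse event related to the use of an investigational medical device".

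Elsewhere the protocol treats the comparator as in scope. A note to the adverse event definition in 9.3 says: "This includes events related to the investigational medical device or the comparator". Section 9.7 has the investigator rate relatedness to the participant's "own insulin pump, study CGM and Omnipod 5", and section 10.3 has the Medical Monitor adjudicate relatedness to the same three devices.

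Other criteria in 9.4 reach Control events whether or not a device caused them. Criterion 3 covers an event not due to a study device issue "which leads to temporary or permanent discontinuation of the study devices or the participant's own insulin pump", or one with a clinically significant effect on glucose control. Criterion 4 is "An AE that affects the participant's ability to complete any study procedures", and criterion 5 is "An AE for which a visit is made to a hospital emergency department". Criteria 6 and 7 bring in the hypoglycemic and hyperglycemic/ketotic events of 9.5 and 9.6.

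Protocol 12.3.1 tabulates events by phase, category, seriousness, severity and relationship to the procedure and the devices. SAP 6.5 uses the same factors but narrows the last one to "relationship to the study procedures and the investigational device".

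**The concern.** The stated purpose is efficacy and safety compared with pump and CGM therapy, and the secondary objective includes comparative safety. If relatedness alone triggers a report for one arm's pump and not for the other's, counts of minor events differ by arm because of the collection rule, even when the true rates are equal. Many of the Pod risks listed in Protocol 9.1 (redness, itching, induration, adhesive reactions) are of this minor kind.

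Rating own-pump relatedness under 9.7 does not solve this, because a rating exists only for an event that has been reported. The planned tabulation by phase has the same gap. Everyone uses their own pump during standard therapy, so in the Intervention arm minor pump-related events would appear to rise after the switch to Omnipod 5. Neither Protocol 12.3.1 nor SAP 6.5 warns of this.

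**Working it through.** **Step 1. Apply each 9.4 criterion to a non-serious, non-glycemic event caused by the pump** (for example a mild site reaction), reading *investigational device* as Omnipod 5.

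| Criterion | Caused by Omnipod 5 (Intervention) | Caused by own pump (Control) |
|---|---|---|
| 1. Serious event | no | no |
| 2. ADE | yes, on relatedness alone | no |
| 3. Device stopped, or glucose control affected | already reportable under 2 | only with that consequence |
| 4. Study procedures affected | already reportable under 2 | only with that consequence |
| 5. Emergency department visit | already reportable under 2 | only with that consequence |
| 6, 7. Glycemic events | same rule in both arms | same rule in both arms |

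The arms differ only through criterion 2, and only for events that trigger none of criteria 3 to 7.

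**Step 2. Check the reading of the device term.**

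- Broad reading: SAP 2.2, headed *Investigational Device*, lists the devices of both arms, including the participant's own pump. The protocol synopsis lists the own pump under *Study Devices*. On this reading criterion 2 reaches the Control pump and the asymmetry disappears.
- Narrow reading: criterion 3 names the study devices and the own pump as separate things. Section 10.1 uses the investigational device for what Intervention participants may be told to stop or to use only in Manual Mode.

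The narrow reading fits the reporting section itself and is the better one. Because both readings have support, sites may also differ in what they report.

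**Step 3. Size, as an illustration.** The plan gives no rate for minor pump-related events, so there is no figure of its own to reproduce here. Its only number used is the randomized total, which checks: 131 / (1 − 0.229) = 169.9, or 170. At 2:1 this is about 113 Intervention and 57 Control.

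Let p be the true proportion of participants with such an event, equal in both arms. All are captured in Intervention, and a share c is captured in Control through criteria 3 to 7. Both p and c are assumptions.

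Spurious difference = p − pc = p(1 − c)

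| p | c = 0 | c = 0.25 | c = 0.5 |
|---|---|---|---|
| 5% | 5.0 points | 3.8 points | 2.5 points |
| 10% | 10.0 points | 7.5 points | 5.0 points |
| 20% | 20.0 points | 15.0 points | 10.0 points |

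At p = 10%, the expected Intervention count is 113 × 0.10 = 11.3. The expected Control count is 57 × 0.10 × c, which is 0, 1.4 or 2.9, against 5.7 with equal capture. If someone ran a Fisher exact test on such a table, the chance of p ≤ 0.05 would be 0.81, 0.33 or 0.12 for c = 0, 0.25 or 0.5, and 0.03 with equal capture. The SAP plans no such test.

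**Step 4. What is untouched.** Severe hypoglycemia and DKA count as serious events under 9.5 and 9.6, whatever the arm. They are the only adverse events with a planned between-arm test (Protocol 12.3.3, SAP 5.2.5, if there are at least 5 events). The effect on that test is zero.

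**The case against.** The strongest reply has four parts.

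- **Consequential Control events are captured.** A reader might infer that no non-serious pump-related event is recorded in Control. The text does not support that. Criteria 3 to 5 and 7 cover stopping the own pump, an effect on glucose control or study procedures, emergency visits, prolonged hyperglycemia with ketones, and hyperglycemia for which the site gave guidance. This stands, and it limits the point to minor events without such consequences.
- **The formal safety comparison is not biased.** A reader might extend the concern to the whole between-arm safety comparison. The tested events and all serious events follow one rule in both arms. The remaining tables are descriptive, and the text does not name treatment group as a factor. This also stands.
- **The term may already include the own pump.** SAP 2.2 and the synopsis give some support. The wording of criterion 3 and section 10.1 weighs against it, so this calls for reconciliation and does not dispose of the point.
- **The direction is conservative.** Extra Intervention events cannot produce a false claim of better safety, and study success depends on time in range alone. That lowers the stakes, but unequal collection still makes the descriptive comparison misleading.

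It is also tempting to set 11 of 113 against 0 of 57 (Fisher p = 0.017), or 17 of 113 against 0 of 57 at a 15% rate (p = 0.0008). These figures assume that nothing is captured in Control and apply a test the plan does not contain, so they should not be quoted as the size of the problem.

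**Conclusion.** The point holds in a limited form. On the better reading of Protocol 9.3 and 9.4, descriptive counts of minor, non-serious device-related events are collected more fully for Omnipod 5 than for the participant's own pump. They are not comparable between arms or, within Intervention, between phases. The difference counts against Omnipod 5.

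The size cannot be known from the documents. It is p(1 − c), or 5 to 10 points at an assumed 10% rate with up to half of Control events captured, and it is zero if criterion 2 is meant to include the own pump. The primary endpoint, the secondary testing hierarchy, serious events, severe hypoglycemia and DKA are unaffected. The change is worth making because comparative safety is a stated objective and the correction is cheap.

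**What to change.** Extend criterion 2 of Protocol 9.4 to adverse events related to any device rated in 9.7, including the participant's own insulin pump, with the same glycemic exclusions. With equal capture the spurious difference is zero: in the 10% illustration, 11.3 of 113 against 5.7 of 57. The cost is a protocol wording change and some extra Control adverse event forms. No sample size figure changes.

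In the same edit, define *investigational device* and *study devices* once, and reconcile the synopsis, Protocol 9.3, 9.4 and 10.1, and SAP 2.2 and 6.5.

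If the data are already collected, state the asymmetry in SAP 6.5. Base any between-arm adverse event comparison on classes captured alike in both arms: serious events, severe hypoglycemia, DKA, other reportable hyperglycemic/ketotic events, and emergency department visits. Add a note to the phase tables. This costs SAP wording only, but it cannot recover minor Control events that were never recorded.
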